## Trial schedule

### START HCQ block

Table 1-1

Visit	Screening evaluations and Visit 1	Visit 2	Email-/Phone-Visit	Visit 3	Email-/Phone-Visit	Visit 4
Action	„Start of baseline“	“End of baseline“ + Day 1 of treatment	Every 7 days at home	End of 1 st Tx period	Every 7 days at home	“End of trial”
Trial day	-28 to -3	1	7, 14, 21 (+/- 3)	28 (-4, +7)	35, 42, 49 (+/- 3)	56 (-4, +7)
Demographics (e.g. sex, age)	X					
Patient information, informed consent	X					
Previous (last 12 months) and concomitant diseases	X	X	X	X	X	X
Previous (last 3 months) and concomitant treatments	X	X	X	X	X	X
Inclusion/exclusion criteria	X	X 				
Pregnancy test K	X*			X		X
Randomization a	X					
Trial medication supply to patient		X		X		
History (cardiotoxicity, hypoglycaemia)	X	X		X		X
Physical examination	X	X		X		X
Vital signs (BP, pulse, temp) b	X	X		X		X
ECG i	X*			X		X
Ophthalmologic review j	X*					X
Lab c (GOT/GPT/Crea/Potassium/CK/gGT/LDH/BB/DIFF / HCQ drug level, blood glucose)	X*			X		X
pO 2 , pCO 2 (capillary)	X	X 		X 		X 
O 2 -sat e , in room air	X	X	X	X	X	X
Respiratory rate, in room air	X	X	X	X	X	X
Retractions	X	X	X	X	X	X
Coughing	X	X	X	X	X	X
Oxygen demand	X	X	X	X	X	X
Chest x-ray	X 			X 		

CONFIDENTIAL

Visit	Screening evaluations and Visit 1	Visit 2	Email-/Phone-Visit	Visit 3	Email-/Phone-Visit	Visit 4
Pulmonary hypertension (Echo) j	X*					
Quality-of-life i	X*			X		X
Health Economics h	X*			X		X
Weight for height b	X*	X		X		X
Clinical course of lung disease	X 	X 	X 	X 	X 	X 
Exacerbation o	X 	X 	X 	X 	X 	X 
Adverse events	X	X	X	X	X	X
Drug accountability				X		X
Additionally in children > 5 years						
Spirometry / Bodyplethysmography a	X	X		X		X
6 minute walking distance (meter) g	X	X		X		X
O 2 -saturation before and after 6MWT	X	X		X		X
Borg scale t	X	X		X		X
Additionally in ventilated patients m						
Oxygenation index (OI) n	X	X	X	X	X	X
Duration (h) of mechanical ventilation	X	X	X	X	X	X
NO (%), ECLS (VV/VA/ECLA/Flow/time since insertion)	X	X	X	X	X	X

X\* Tests must be done before first drug dosing

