## STOP HCQ block

Table 1-2

Visit	Visit 1 + Screening	Visit 2	Email- /Phone- Visit	Visit 3	Email-/ Phone- Visit	Visit 4	Email-/ Phone- Visit	Visit 5	Email-/ Phone- Visit	Visit 6	Email- /Phone- Visit	Visit 7	Email- /Phone- Visit	Visit 8
Action	„Begin of baseline“	“End of baseline“ + Day 1 of withdrawal treatment	2 weeks of withdrawal, at home	4 weeks of withdrawal treatment	6 weeks of withdrawal, at home	8 weeks of withdrawal treatment	10 weeks of withdrawal, at home	“End of trial“ after 12 weeks of withdrawal treatment	2 weeks of open observation at home	Follow up after 4 weeks of open observation	6 weeks of withdrawal, at home	Follow up after 8 weeks of open observation	10 weeks of withdrawal, at home	Follow up after 12 weeks of open observation
Trial day	-30 to -10	1	14 (-7, +7)	28 (-7, +7)	42 (-7, +7)	56 (-7, +7)	70 (-7, +7)	84 (-7, +7)	98 (-7, +7)	112 (-7, +7)	126 (-7, +7)	140 (-7, +7)	154 (-7, +7)	168 (-7, +7)
Demographics (e.g. sex, age)	X													
Patient information, informed consent	X													
Previous (last 12 months) and concomitant diseases	X	X	X	X	X	X	X	X	X	X	X	X	X	X
Previous (last 3 months) and concomitant treatments	X	X	X	X	X	X	X	X	X	X	X	X	X	X
Inclusion/exclusion criteria	X	X 												
Pregnancy test k	X*			X		X		X						
Randomization a	X													
Trial medication supply to patient		X		X		X								
History (cardiotoxicity, hypoglycaemia)	X	X		X		X		X		X		X		X
Physical examination	X	X		X		X		X		X		X		X
Vital signs (BP, pulse, temp) b	X	X		X		X		X		X		X		X
ECG j	X*							X						X
Ophthalmologic review l	X*													X 
Lab c (GOT/GPT/Crea/Potassium/CK/gGT/LDH/BB/DIF F / HCQ drug level, blood glucose)	X*			X		X		X		X (only HCQ drug level)		X (only HCQ drug level)		X (only HCQ drug level)
pO 2 , pCO 2 (capillary)	X	X 		X 		X 		X 		X 		X 		X 
O 2 -sat e , in room air	X	X	X	X	X	X	X	X	X	X	X	X	X	X
Respiratory rate, in room air	X	X	X	X	X	X	X	X	X	X	X	X	X	X

CONFIDENTIAL

Visit	Visit 1 + Screening	Visit 2	Email- /Phone- Visit	Visit 3	Email-/ Phone- Visit	Visit 4	Email-/ Phone- Visit	Visit 5	Email-/ Phone- Visit	Visit 6	Email- /Phone- Visit	Visit 7	Email- /Phone- Visit	Visit 8
Retractions	X	X	X	X	X	X	X	X	X	X	X	X	X	X
Coughing	X	X	X	X	X	X	X	X	X	X	X	X	X	X
Oxygen demand c	X	X	X	X	X	X	X	X	X	X	X	X	X	X

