a Randomization must occur for logistic reasons as soon as possible after concluding all screening investigations and including the patient into the study. This secures delivery of the study medication in time to any study center.

b Weight (kg) and height (cm) will be measured with shoes and clothes off. Vital signs will be collected after the patient has been at rest for 5 minutes.

c Blood sample should include: Blood count with differential, GOT, GPT, gGT, Creatinine, LDH, Potassium, Creatine kinase, blood glucose. HCQ drug level (2 ml EDTA blood and 2 ml of Serum blood). Labor Manual will be provided.

d Spirometry / Bodyplethysmography will be performed pre-bronchodilator in children age  $\geq$  5 years. (If a child  $\leq$  5 years is already able to perform the listed investigations (spirometry or bodyplethysmography), these should also be performed and documented at the discretion of the investigator) The following lung function parameters will be assessed: FEV1 % predicted (recorded in L), FEV 1 (L), FVC % predicted (recorded in L), FVC (L); MEF 75 (L/s); MEF 50 (L/s); MEF 25 (L/s); TLC (L); ITGV (L); RV (L); R eff (kPa\*s/L); R eff predicted (%). SOP will be provided.

e Measurement of O2-Saturation, respiratory rate and O2 flow (if necessary) in awake patient at rest:

If not on O2: after 5 min at rest, room air, then measure twice over 1 min. each; the measurements have to be at least 1 min. apart; report the stable average value

If on O2:

- BEFORE withdrawal (after 5 min at rest with steady state O2 supplement, measure over 1 minute)
- Then withdraw O2 to obtain steady state O2-Sat. in room air (at least 30 seconds without change). Then measure twice over 1 min. each; the measurements have to be at least 1 min. apart; report the stable average value. If the O2-Sat falls below SpO2<80% place back in oxygen and note as exact value.

Document the time of measurement and state of the patient, usually "awake, at rest". Note: In babies avoid crying, eating, sleeping during measurement. Note: try to schedule patients at similar time of the day.

f Borg-Scale: assessment of dyspnea (0 – 10: 0 = no dyspnea at all, 5 = severe dyspnea, 10 = extremely severe dyspnea)

g Standard exercise testing (6-minute-walk test): SOP will be provided

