### Safety monitoring

Adverse events, clinical laboratory values (GOT, Creatinine, gGT, blood count, differential, LDH, potassium, steady state drug level), ECG, ophthalmologic review

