## 8.5 Analysis of clinical laboratory findings

Listings will be prepared for each laboratory measure and will be structured to permit review of the data per subject as they progress on treatment. Summary tables will be prepared to examine the changes of laboratory measures over time. Additionally, shift tables will be provided to examine the changes of laboratory data from normal baseline to values outside the corresponding reference range during/after treatment.

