4.2.1 Efficacy

The following variables will be investigated:

- Oxygen saturation (O2-sat, in room air) (only absolute, as relative already primary outcome) assessed at every visit (not web/tele feedback)
- Respiratory rate (RR, in room air) (relative and absolute) assessed at every visit and every web/tele feedback
- Retractions (yes/no) assessed at every visit and every web/tele feedback
- Coughing last 24 h (yes/no) assessed at every visit and every web/tele feedback
- Oxygen requirement assessed at every visit and every web/tele feedback
- pO2, pCO2 (capillary, in room air)
- Chest x-ray scoring for chILD assessed at screening and visit 3 (START HCQ Block) and visit 5 (STOP HCQ Block)
- Overall survival
- If > 5y old
 - FEV1 % predicted (recorded in L)
 - FVC % predicted (recorded in L)
 - reference values according to the GLI 2012 lung function regression equations
 - 6 minutes walking distance (meter)
 - O2-saturation before and after 6MWT
 - Borg scale
- If ventilated:
 - Duration (h) of mechanical ventilation
 - NO (%), ECMO yes/no, if yes VA/VV, double lumen vs. single lumen, Flow-rate.

4.2.2 *Safety/Tolerability*

Adverse events, clinical laboratory values (GOT, Creatinine, gGT, blood count, differential, LDH, BNP, steady state drug level), ECG, ophthalmologic review

Adverse events will be documented during the study at each visit (exemption: START HCQ between Visits 1 and 2. However, occurring AEs between those visits are not treatment emergent).

Laboratory data will be assessed at screening, visit 3 and visit 4 in the START HCQ Block and at screening, visit 3, 4 and visit 5 and EDTA additionally at visit 6 in the STOP HCQ Block.

Vital signs (respiratory rate, height, weight, BMI, heart rate, blood pressure (systolic and diastolic), temperature, hypoglycaemia (yes/no), appropriate observation of blood glucose levels (yes/no), cardiotoxicity (yes/no), appropriate ECG (yes/no)) will be assessed at screening, and every following visit (not web/tele feedback).

A physical examination will be done at the same visits.

Symptoms and clinical course of treatment will be documented at the same time points as the physical examination is performed and at telephone contact visit.

4.2.3 *Quality of Life (Peds QL)*

Not applicable.

4.2.4 *Health Economics*

Not applicable.

5 Treatment of Missing Values and Outliers

5.1 *Missing Values*

No substitution of missing values is planned.

5.2 *Outliers*

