6.7.2.2 Laboratory Parameters

Listings will be prepared for each laboratory measure and will be structured to permit review of the data per subject as they progress on treatment.

Summary tables will be prepared to examine the changes of laboratory measures over time by descriptive statistics and exploratory p-values.

6.7.2.3 *Vital Signs*

Absolute values and changes from baseline of the vital signs will be analysed descriptively and by exploratory p-values.

6.7.2.4 *Others*

Not applicable.

6.7.3 *Quality of Life (Peds QL)*

Each item will be reversed scored and linearly transformed to a 0-100 scale as follows:

0=100, 1=75, 2=50, 3=25 and 4=0 (higher scores indicate better quality of life).

If more than 50% of the items in a scale are missing, the scale score should not be computed.

Mean scores are defined as sum of the items over the number of items answered.

The psychosocial health summary score is the sum of the items over the number of items answered in the emotional, social and school functioning scales.

The total score is the sum of all items over the number of items answered on all the scales.

Descriptive statistics and exploratory p-values (t-tests with unequal variances) for absolute values and changes to baseline will be tabulated.

6.7.4 *Health economics*

The analysis will not be done by the IZKS.

6.8 *Subgroup Analyses*

Not applicable.

6.9 *Interim Analysis*

No interim analysis is planned.

7 Software

All analyses will be performed using the Statistical Analysis Software (SAS), Version 9.4.

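### The SAP's safety laboratory list names BNP, which no visit samples, where the protocol has potassium, and the SAP drops the protocol's laboratory shift tables without a reason

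*SAP*

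**What the plan says.** **Safety variable lists.** SAP 4.2.2 names "clinical laboratory values (GOT, Creatinine, gGT, blood count, differential, LDH, BNP, steady state drug level". The corresponding protocol list, under Safety monitoring in 3.4, reads "clinical laboratory values (GOT, Creatinine, gGT, blood count, differential, LDH, potassium, steady state drug level".

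**What is sampled.** The protocol's START schedule (Table 1-1) gives the panel as "GOT/GPT/Crea/Potassium/CK/gGT/LDH/BB/DIFF / HCQ drug level, blood glucose", and the STOP schedule (Table 1-2) has the same analytes. Footnote c, which serves both tables, lists "Blood count with differential, GOT, GPT, gGT, Creatinine, LDH, Potassium, Creatine kinase, blood glucose" and then the HCQ drug level. The full panel is taken at screening and Visits 3 and 4 in START, and at screening and Visits 3, 4 and 5 in STOP. STOP Visits 6 to 8 are marked "X (only HCQ drug level". The SAP's own schedules show BUN in the place of potassium. Its footnote c also has BUN, and leaves out glucose.

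**What is analysed.** Protocol 8.5 plans listings, summaries of change over time and, in addition, that "shift tables will be provided to examine the changes of laboratory data from normal baseline to values outside the corresponding reference range". SAP 6.7.2.2 keeps the listings for every laboratory measure and then says "Summary tables will be prepared to examine the changes of laboratory measures over time by descriptive statistics and exploratory p-values". It does not mention shift tables and gives no reason for leaving them out.

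**The concern.** A safety variable list tells the programmer what to tabulate and tells the reader what was promised. This one promises an analyte for which the visit schedules will produce no data. It also leaves out potassium, which the protocol both samples and names as a safety variable. Protocol 4.1.1.5 gives hypokalaemia as a sign of overdose, so potassium is not an incidental item.

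The missing shift tables affect every analyte. The protocol judges laboratory safety mainly by limits: section 1.4 speaks of deviations that are usually more than twice the upper limit of normal. Patients range from 3 weeks of age to adulthood, and the protocol itself sets GFR limits by age in 3.6.2. A table of movement from normal to outside the reference range suits that setting better than average change pooled over all ages.

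**Working it through.** The plan states no figure to reproduce, so the check is an item-by-item comparison of the laboratory lists.

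| Item | Protocol panel (Tables 1-1, 1-2, footnote c) | Protocol 3.4 | SAP schedules | SAP footnote c | SAP 4.2.2 |
|---|---|---|---|---|---|
| GOT, creatinine, gGT, LDH, blood count, differential, drug level | yes | yes | yes | yes | yes |
| GPT, CK | yes | no | yes | yes | no |
| Blood glucose | yes | no | yes | no | no |
| Potassium | yes | yes | no | no | no |
| BUN | no | no | yes | yes | no |
| BNP | no | no | no | no | yes |

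**Differences between the lists**

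- Protocol 3.4 (8 items) against SAP 4.2.2 (8 items): 7 in common. Potassium is only in the protocol and BNP only in the SAP.
- Protocol panel (11 items) against SAP 4.2.2 (8 items): 7 in common. 11 − 7 = 4 sampled but not listed (potassium, GPT, CK, glucose); 8 − 7 = 1 listed but not sampled (BNP).
- Protocol panel (11 items) against SAP schedule panel (11 items): 10 in common. Potassium is only in the protocol and BUN only in the SAP.

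The SAP's departure from the protocol's safety list is therefore one analyte. The absence of GPT, CK and glucose is inherited from protocol 3.4.

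**Analysis text.** Of the three outputs in protocol 8.5 (listings, summaries over time, shift tables), SAP 6.7.2.2 keeps the first two, adds exploratory p-values and drops the third. SAP 4.1 defines each laboratory parameter as a value with a normal/abnormal result, marked as measured at later visits too. The data for a shift table are therefore already planned.

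**What a shift table adds to a comparison of means.** The planned 80 subjects, an equal split between blocks and 1:1 allocation give 80 / 2 / 2 = 20 per arm. Assume, for illustration only, that 2 of 20 children have a CK rise of k SD and the others do not change.

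- Shift in the arm mean = 2k / 20. With k = 3 it is 0.3 SD; with k = 5 it is 0.5 SD.
- Variance in that arm is about 1 + 0.1 × 0.9 × k², which is 1.81 for k = 3 and 3.25 for k = 5.
- Standard error of the difference is about √((1.81 + 1)/20) = 0.37 and √((3.25 + 1)/20) = 0.46.
- The t statistic is about 0.8 for k = 3 and 1.1 for k = 5, so the exploratory p-value would flag neither.
- If both children began normal and ended out of range, a shift table shows 2/20 = 10% in either case.

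The k values are not from the documents. The illustration concerns the mean and its p-value only. The maximum and the per-subject listing would still show the extreme values.

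**The case against.** A reader might infer that several markers of HCQ toxicity will not be analysed. The documents do not support that. SAP 6.7.2.2 covers every laboratory measure and is not tied to the list in 4.2.2, and GPT, CK and glucose are in the SAP's own schedules. For hepatic damage, GOT and gGT are on the list. Hypoglycaemia is recorded yes/no under vital signs in SAP 4.2.2, together with an item on observation of blood glucose. Even potassium would be listed and summarised if it is in the database.

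A reader might also infer that without shift tables only mean changes remain. That is not so. The defaults in SAP section 6 include median, quartiles, minimum and maximum by treatment group, and counts and percentages for qualitative variables. The normal/abnormal result could be tabulated by visit under that default. What is lost is the link between a child's baseline status and later status.

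Nor should it be said that every laboratory draw includes the four unlisted analytes, because STOP Visits 6 to 8 take the drug level alone. BNP may be a slip for BUN, but the documents do not settle this, and either reading leaves potassium out.

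Finally, protocol section 8 lets the SAP modify the protocol's plans, and the trial is exploratory, so dropping the shift tables is not forbidden. The same section requires deviations to be described and justified in the final report, and the SAP gives no reason.

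These points limit the consequence. They do not remove the BNP entry, the absence of potassium from the whole SAP, or the unexplained loss of the shift tables.

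**Conclusion.** The point holds as a matter of consistency and of one missing analysis. One listed safety variable (BNP) has no sampling behind it. One sampled analyte that protocol 3.4 names (potassium) is absent from the whole SAP. Three others (GPT, CK, glucose) are drawn but listed as safety variables in neither document, with no loss of listings or summaries. For all analytes, the planned cross-tabulation from normal baseline to out of range is gone without explanation.

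This rests on reading SAP 6.7.2.2 as applying to all laboratory measures in the database, and on the protocol panel being the one in use. If the database follows the SAP schedules, potassium may not be there at all, and the gap for that analyte would be larger. The documents do not show which applies.

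**What to change.** - **SAP 4.2.2:** replace BNP with potassium, add GPT, CK and blood glucose, and keep the HCQ drug level, which a secondary objective in both blocks needs.
- **SAP schedules and footnote c:** align with the current protocol panel, with potassium for BUN, and add glucose to the footnote.
- **Protocol 3.4:** add GPT, CK and glucose to the safety monitoring list so that both lists match what is sampled.
- **SAP 6.7.2.2:** restore the protocol 8.5 shift tables, by arm and visit, using the normal/abnormal result already defined in SAP 4.1. The post-baseline visits with a full panel are Visits 3 and 4 in START and Visits 3, 4 and 5 in STOP, so 2 + 3 = 5 visits in all. If the sponsor still prefers to omit them, the reason belongs in the SAP and the final report.

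The cost is wording in both documents and one extra set of standard tables. No new samples are needed. The changes should be made before the blind is broken.

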X Test can be done according to the opinion of the treating physician

X Puncture site should be warm and well perfusedp.

X Chest x-ray is recommended if clinically indicated e.g. to answer the question if the disease is stable

X Re-check inclusion criteria 1

X (since last visit): Healthy / Sick-better / Sick-same / Sick-worse / Patient died

X Pulmonary exacerbation is defined as sustained worsening of the patient's condition from stable state and beyond normal day to day variations. The exacerbation is rated as indicated belowo.

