### 3.6 Selection and withdrawal of subjects

#### 3.6.1 Inclusion criteria

For block specific inclusion criteria please see synopsis.

Subjects meeting the block specific inclusion criteria and all of the following criteria will be considered for admission to the trial:

1.	
Patients should be clinically stable during baseline (between Visit 1 and 2) for inclusion into the study
 
a) To determine this, attending physicians can use SpO2 in room air for patients on room air or on O2-supplement; the absolute difference on SpO2 is expected not to be <math>\geq 5\%</math> between Visit 1 and 2. For patients on respiratory support, the summary key parameters should not change <math>\geq 20\%</math> between Visit 1 and 2
 
and
 
b) No major changes in other medications between Visit 1 and 2

2.	
Mature newborn <math>\geq 37</math> weeks of gestation, age <math>\geq 3</math> wks and <math>< 2</math>y
 
or
 
Infants and children (<math>\geq 2</math> y and <math>< 18</math> y)
 
or
 
Adults (<math>\geq 18</math> and <math>\leq 30</math> y)
 
or
 
Previously preterm (<math>\leq 37</math> weeks of gestation) babies or children and adults of all ages if chILD genetically diagnosed (see inclusion criterion 3.)

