### 8.2 Analysis populations

All subjects with signed informed consent are considered as enrolled subjects, even if they did not receive any trial treatment. All randomised subjects will be included in the Intention-to-treat (ITT) population. This population is the primary analysis population. Within ITT population analyses subjects will be assigned to the treatment to which they were randomised. For the combined analysis the ITT Population consists of all patients that are at least in the START or the STOP block. The corresponding PP Populations consist of the patients from the ITT population without major protocol violations. Major protocol violations will be defined in the SAP. The safety population comprises all subjects who received at least one dose of trial treatment. In analyses of the safety population subjects will be assigned to the treatment which they actually received. The analysis populations will be defined prior to unblinding of the study.

For analysis, subgroups of patients will be defined, based on age, categories of diagnosis and further appropriate factors.

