2.2 Scope

The primary population for the analyses of efficacy are the ITT Populations (randomised patients) for each block. For the combined analysis the ITT Population consists of all patients that are at least in the START or the STOP block.

Safety parameters will be analysed based on the safety population for the assessment of safety.

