6.6 Primary Analysis

The variable assessing the primary outcome is the response rate measured by the oxygen saturation in room air.

START HCQ block

Relative change from trial day 1 (Visit 2) to day 28 (Visit 3) and day 56 (Visit 4) and from day 28 to day 56 change from active compound compared to change from placebo

STOP HCQ block

Relative change from trial day 1, i.e. Visit 2, through day 84, i.e. Visit 5: change from active compound compared to change from placebo

Both blocks separately

a) A difference between the changes in placebo and active phases is considered significant as described in the table below.

Patient's condition	Measured parameter	Definition of significant change or responder
Stable in room air or on	SpO2 in room air	Increase $\geq 5\%$

O2-supplement		
On high-flow nasal cannula	O2-flow, air-flow	Decrease $\geq 20\%$ or support not needed any more
Ventilated	Oxygenation index	Decrease $\geq 20\%$ or support not needed any more
On ECMO		Decrease $\geq 20\%$ or support not needed any more

The analysis will be done first by discarding the information on the patient's condition. Descriptive analyses will be done overall and for all patients conditions separately.

b) Patients are defined as responder as described in the table above. The numbers of responders are counted and compared by Fisher's exact test as well as logistic regression models with factors for treatment group and age group.

The following SAS code can be used:

```
PROC LOGISTIC DATA=indata;
  CLASS treatment age_gr;
  MODEL responder_YN = treatment age_group treatment*age_group;
RUN;
```

Both blocks together

Not applicable. There were too few patients in both blocks.

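### The primary responder comparison is labelled intention-to-treat, but children who die, are withdrawn or miss the endpoint visit have no responder status, so it would most likely be run on observed cases

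*SAP*

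**What the plan says.** **Population.** Protocol 8.2 states: "All randomised subjects will be included in the Intention-to-treat (ITT) population". SAP 2.2 repeats it: "The primary population for the analyses of efficacy are the ITT Populations (randomised patients) for each block".

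**Missing data.** SAP 5.1 is one sentence: "No substitution of missing values is planned". SAP section 6 makes patients with non-missing data the default basis for qualitative variables, with a category for missing values only where appropriate. It calls a value missing only when the visit was attended. A child who died or left before the visit falls outside even that definition.

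**Analysis.** SAP 6.6 says "The numbers of responders are counted and compared by" Fisher's exact test and logistic regression, with the code "MODEL responder_YN = treatment age_group treatment*age_group". It gives no denominator and no rule for an undetermined response. SAP 2.3 drops the per-protocol analysis, and no missing-data sensitivity analysis is planned.

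**Withdrawal.** Protocol 3.6.3 lists life-threatening aggravation, adverse events and death among the reasons for withdrawal. Withdrawn subjects are not replaced. Final-day examinations are to be done as far as possible, but nothing links them to responder status. Protocol 3.5.2 requires unblinded patients to be withdrawn.

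**The concern.** An intention-to-treat comparison of responder proportions needs a status for every randomised child. This plan defines the population but not the status. Its defaults lead to an analysis of children who reached the endpoint visit.

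That is harmless only if reaching the visit is unrelated to outcome within each arm. The withdrawal reasons make this doubtful: a child who deteriorates or dies is both more likely to be missing and unlikely to have been a responder. If such losses differ between arms, the responder difference shifts, upward when HCQ loses more non-responders and downward when placebo does. The result would still be reported as ITT.

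**Working it through.** **Is there a rule anywhere?** The places that could hold one are SAP 4.2, 5.1, 6 and 6.6, and protocol 3.6.3 and 8.2 to 8.3.1 with Table 3.8-1. Death appears in overall survival, in the clinical-course category and in the adverse-event tables, but never in the responder definition. Discontinuation reasons are tabulated (SAP 6.1), not used.

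**Which sample do the analyses use?** For the logistic model it is children with a response: the SAS procedure excludes records with a missing response by default, and the code does not change that. For Fisher's test the denominator is not stated, but the section 6 default points to the same children.

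**Inputs.**
- Planned number: 80, with no formal calculation (protocol 8.1). There is no sample-size figure to reproduce.
- Equal split between blocks (protocol 3.2) and 1:1 allocation (protocol 3.5.1): 80 / 2 / 2 = 20 per arm per block. One child is 1/20 = 5 points of an arm's rate.
- Response and loss rates: the documents give none. Assumed for START: 8 HCQ and 3 placebo responders, and every lost child a non-responder.

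**Formulas.** With a and b responders and m1 and m0 children lost:
- difference = a/(20 − m1) − b/(20 − m0)
- crude OR = [a/(20 − m1 − a)] / [b/(20 − m0 − b)]

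Example, two lost from HCQ: 8/18 − 3/20 = 44.4% − 15.0% = 29.4 points; OR = (8/10)/(3/17) = 4.53.

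| Lost (HCQ, placebo) | Compared | Difference | Crude OR | Fisher p |
|---|---|---|---|---|
| 0, 0 | 8/20 vs 3/20 | 25.0 points | 3.78 | 0.155 |
| 2, 0 | 8/18 vs 3/20 | 29.4 points | 4.53 | 0.074 |
| 0, 2 | 8/20 vs 3/18 | 23.3 points | 3.33 | 0.160 |
| 1, 1 | 8/19 vs 3/19 | 26.3 points | 3.88 | 0.151 |
| 2, 2 | 8/18 vs 3/18 | 27.8 points | 4.00 | 0.146 |

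**Range.** With 0 to 3 non-responders lost per arm, the difference runs from 22.4 (8/20 vs 3/17) to 32.1 points (8/17 vs 3/20). If two children per arm have unknown status, the bounds are 8/20 vs 5/20 = 15.0 points and 10/20 vs 3/20 = 35.0 points.

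**Other assumed rates, two lost from one arm.** 6/20 vs 2/20 (20.0 points) becomes 23.3 or 18.9. 10/20 vs 5/20 (25.0 points) becomes 30.6 or 22.2.

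**Limits.** The odds ratios are crude. The SAP model includes a treatment-by-age-group interaction, so it yields no single treatment odds ratio. No STOP figure is given, because SAP 6.6 defines response only as improvement, while the withdrawal column of protocol Table 3.8-1 defines it as worsening.

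**The case against.** **The stakes are limited.** Protocol 1.2 calls the study explorative, there is no sample-size calculation and p-values are exploratory. Losses, deaths and discontinuations are reported, so a reader would see an imbalance. Balanced loss moves the estimate little (25.0 to 26.3 or 27.8 points), and all the rates are assumed. This stands, and it limits the point to the credibility of the estimate. But tabulating losses does not repair the comparison, and a denominator chosen after unblinding is open to the data.

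**Not every missing saturation leaves a child unclassified.** Table 3.8-1 also uses respiratory rate and support status. That is right for children who attend. It does not help for those who died or had no visit.

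**Stronger readings that the documents do not support:**
- *Fisher's test and the logistic model will use different samples.* This needs Fisher's test to run over all randomised children. The wording allows it, but the section 6 default makes it the less likely reading.
- *Escalation from room air to more support has no line in either document.* For STOP, Table 3.8-1 lists new need for support in the withdrawal column of the supported rows, which can be read as covering a child coming from room air. In START, escalation meets no improvement criterion. What is unclear is which row applies.
- *The Visit 2 check will leave randomised children without data.* Protocol footnote a says "Randomization must occur for logistic reasons as soon as possible after concluding all screening investigations", while note X5 to Table 1-1 for Visit 2 reads "Re-check inclusion criteria 1", and that criterion is "Patients should be clinically stable during baseline (between Visit 1 and 2) for inclusion into the study". So a child can fail it after randomisation. But neither document says that such a child is withdrawn or left undosed, and the check itself normally yields a Visit 2 saturation.

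**Conclusion.** The point holds as a gap that should be fixed. Followed as written, the plan most likely gives an observed-case comparison under an ITT label. Under the assumed START counts, two non-responders lost from one arm move a 25.0-point difference to between 23.3 and 29.4 points, and two unknowns per arm leave it anywhere from 15.0 to 35.0. These sizes rest on 20 per arm and on assumed response and loss rates. The gap itself rests only on the text.

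A reader might infer inflated type I error, because one child can carry a p-value across 0.05: with assumed counts, 8/19 vs 2/20 gives 0.031 and 8/20 vs 2/20 gives 0.065. The documents set no significance level for the trial and treat all p-values as exploratory, so no error rate is lost.

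**What to change.** State the following in the SAP before unblinding.

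1. **Denominator.** All randomised children in the block, for both Fisher's test and the logistic model.
2. **Status.** Count death, withdrawal for disease aggravation, and any child with no determinable status at Visit 3 or Visit 5 as non-response in START and as deterioration in STOP. First reconcile the STOP direction in SAP 6.6 with Table 3.8-1: under the protocol definition, scoring a death in STOP as non-response would make it count as favourable. Also state which row of Table 3.8-1 applies when support escalates from room air.
3. **Sensitivity analyses.** Observed-case, best- and worst-case, and exclusion of children never dosed.

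Do not replace a missing Visit 2 baseline with the Visit 1 value in the primary analysis. Inclusion criterion 1 tolerates a Visit 1 to Visit 2 difference of just under 5 points, about the size of the responder threshold. For example, with 90% at Visit 1, 94% at Visit 2 and 95% at Visit 3, the change is 1 point (1/94 = 1.1%) from Visit 2 but 5 points (5/90 = 5.6%) from Visit 1, so the substitution creates a responder. Use it, and early withdrawal examinations, at most in sensitivity analyses.

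**Cost.** SAP wording, a few lines of code and three or four tables, from data already scheduled for collection. A few children are classified by rule, and counting never-dosed children as failures dilutes the difference slightly. In the illustration, one such child per arm gives 25.0 rather than 26.3 points.

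A separate, minor item: SAP 4.2 notes room-air saturation under 80% only as below that limit, while protocol footnote e asks for the exact value. The two should be reconciled.
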